Data will be electronically scanned into databases and will be double checked by hand. Hard copy documents will be examined to verify questionable observations. Missing data will be examined for each variable. Histograms, normal probability plots, and numerical summaries (skewness, kurtosis) will be used to examine distributional assumptions required for the mixed model analysis described below. Transformations such as the logarithm, square root, and reciprocal will be considered in the event the normality assumption is inadequate. Residual analysis will also be performed to evaluate distributional variance and linearity assumptions. Data analysis will be conducted in collaboration with [name], statistician in the department of Psychiatry and [name] faculty member of the Department of Biostatistics at Yale University School of Public Health. For all analyses, an alpha threshold of 5% (two-sided) will be used to test for statistical significance and will be performed using SAS v9.3 (SAS Institute, Cary, NC).

Analyses will be performed according to the intent-to-treat (ITT) principle where data from any randomized subjects will be analyzed. We will calculate descriptive statistics for participants at baseline, and compare naltrexone to placebo participants using analysis of variance (ANOVA) for normally distributed covariates and chi-square tests for categorical covariates. The impact of baseline variables that demonstrate clinically relevant group differences will be assessed in supportive analyses using covariate adjustment.

Approach to Missing Data: The primary analysis method will use a likelihood-based mixed model, which accommodates incomplete observations and operates under the assumption that the missing data is missing at random (MAR). Missing data patterns, time to withdrawal and reasons for dropout will be compared between the two naltrexone and placebo groups. T-tests, cross-tabulations, and logistic regression will be used to evaluate whether withdrawal is dependent on any observed variables. Finally, should missing data patterns and reasons for missing data suggest a bias or confounding, we will conduct sensitivity analyses using pattern mixture models to examine the influence that dropout bias (informative missingness) may have on treatment differences. Multiple imputation (MI) will also be used in the case of data not MAR. Sensitivity analyses will be performed secondarily among study completers.

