Hypothesis Testing: The primary goal of this study is to compare the weight changes resulting from two different doses of naltrexone compared to placebo. The primary ITT analysis will employ a linear mixed effects model (LMM) to determine the effect of treatment status (between-subjects for: naltrexone 25/50mg vs. placebo) on the trajectory of weight change over time (within-subjects for: study time points). The interaction between treatment and time will be modeled and interpreted using graphical displays and post-hoc contrasts on least square means. The latter will include estimation of group contrasts at each time point and polynomial (linear, etc.) contrasts for time within each group. However, the primary contrasts will be each dose compared with control at 52 weeks. Because the outcome data are correlated (i.e., weight assessed from the same subject at different time points), weight over time will be modeled through the inclusion of random subject effects and/or structured variance-covariance matrices, with the best-fitting structure determined by Bayesian-Schwartz Information criteria (BIC). Supportive analyses will also include covariate adjustment for clinically significant variables (as determined from baseline evaluations and also other treatment variables, such as sessions attended). The above model will be fit using SAS PROC MIXED (Cary, NC), using restricted maximum likelihood (REML). The effect of treatment assignment on the secondary outcomes, such as BMI, waist circumference, serum lipid profile, fasting glucose, and glycosylated hemoglobin (HbA1c) will be evaluated using the linear mixed modeling approach described above. The proportion of subjects achieving 3, 4, or 5% weight loss will be compared between the treatment groups with the Fisher's Exact test. Type 1 error for secondary outcomes will be adjusted using the Bonferroni correction, basing the adjustment on the number of conceptually related statistical tests.

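### The only analysis that departs from missing-at-random runs only if the observed dropout data suggest bias, and observed data cannot rule out informative dropout

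*Combined protocol and SAP*

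**What the plan says.** All of this is in the combined protocol and SAP, Section V, item 12 (Statistical Considerations).

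- **Primary model.** Under Approach to Missing Data, a likelihood-based mixed model is primary and is stated to assume MAR. Under Hypothesis Testing, "the primary contrasts will be each dose compared with control at 52 weeks". The analysis is intention-to-treat and covers every randomized subject.
- **Checks on dropout.** "Missing data patterns, time to withdrawal and reasons for dropout will be compared between the two naltrexone and placebo groups". In addition, "T-tests, cross-tabulations, and logistic regression will be used to evaluate whether withdrawal is dependent on any observed variables".
- **Trigger.** "Finally, should missing data patterns and reasons for missing data suggest a bias or confounding, we will conduct sensitivity analyses using pattern mixture models".
- **Imputation.** "Multiple imputation (MI) will also be used in the case of data not MAR".
- **Completers.** "Sensitivity analyses will be performed secondarily among study completers". This is the only missing-data sensitivity analysis planned without a condition.

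The plan does not say what counts as suggesting bias. It states no shift, reference arm or identifying restriction for the pattern-mixture model or the imputation. It also does not say whether the treatment effect at week 52 is meant to include weight after a subject has left.

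**The concern.** The trigger asks the observed data a question that they cannot answer. MAR and MNAR differ in how the unseen weights behave once the observed ones are taken into account. Dependence of withdrawal on observed variables is compatible with MAR, and its absence does not exclude MNAR. Recorded reasons are more useful, but they are evidence about the unseen weights and not a view of them.

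Subjects who leave early have no week-52 weight, so both primary contrasts depend on what is assumed about them. The protocol itself gives a reason to take this seriously. The Background section cites a study of naltrexone in bipolar women in which weight on average went back to baseline after active treatment stopped. If regain happens after the last visit, a model fitted to weights before dropout does not see it. Under the stated rule, a trial with informative dropout but unremarkable patterns and reasons would report both contrasts with no MNAR analysis.

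**Working it through.** The documents give 200 subjects in a 1:1:1 ratio (about 67 per arm). Neither the statistical section nor the rest of the plan states a 52-week dropout rate, SD, planning effect or power. There is therefore no planned figure to reproduce, and the main check is one of logic.

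**Step 1: what each branch delivers.**

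| Checks | Analyses of the week-52 contrasts | Departs from MAR? |
|---|---|---|
| Look clean | Mixed model, with its covariate-adjusted variants | No |
| Look clean | Completers only | No; generally needs a stronger assumption than the mixed model |
| Flagged | Pattern-mixture model added | Yes, but its restriction is not stated |
| Flagged | Multiple imputation added | Only if a shift, reference arm or restriction is specified; otherwise it repeats MAR |

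**Step 2: can clean checks exclude MNAR?** Take two trials with identical recorded weights, dropout times and reasons. In the first, leavers' later weights follow the MAR prediction. In the second, naltrexone leavers end D kg heavier than predicted. Every planned check uses recorded data only, so it gives the same answer in both. Clean checks therefore cannot exclude the second trial.

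**Step 3: illustration of size. Every value of p and D is an assumption.** If the target includes weight after leaving, with p the share leaving and D the kg by which leavers end worse than MAR predicts:

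bias of the MAR contrast = p(naltrexone) × D(naltrexone) − p(placebo) × D(placebo)

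A positive value overstates the benefit of naltrexone. For D, borrow the 8-week pilot difference: 2.45 + 0.47 = 2.92 kg. With p = 30% in both arms:

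- D = 2.92 in naltrexone only: 0.30 × 2.92 = +0.88 kg
- D = 2.92 in both arms: 0.88 − 0.88 = 0
- D = 2.92 in placebo only: −0.88 kg

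Nothing supports 2.92 kg as an upper or a typical value. The Background gives 1.2 kg against 0.8 kg for naltrexone alone over 24 weeks. D = 0.4 would give 0.30 × 0.4 = 0.12 kg. It also gives a 4.98 kg loss for the pilot's non-diabetic naltrexone subjects. D = 4.98 would give 0.30 × 4.98 = 1.49 kg.

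A simulation agreed with the first case. It used 67 per arm, 30% dropout in both arms unrelated to any observed value, an assumed SD of 4.95 kg, and naltrexone leavers losing the whole 2.92 kg. The contrast in the observed data averaged 2.92 kg and the contrast in all randomized subjects 2.03 kg. A Fisher test of dropout by arm flagged about 3% of trials.

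**Step 4: a visible imbalance can also pass.** This step assumes that suggesting bias means p < 0.05, borrowed from the plan's general rule: "For all analyses, an alpha threshold of 5% (two-sided) will be used to test for statistical significance". With 67 per arm, a chi-square test comparing dropout in two arms flags:

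- 20% v 30%: 27% of trials
- 20% v 35%: 50%
- 20% v 40%: 72%

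**The case against.** The strongest reply is that the trigger is a judgement on patterns and reasons, not a significance test. A statistician could see that many leavers in every arm cite weight gain, and run the pattern-mixture model although the arms do not differ. Weight is measured weekly for four weeks and then every two weeks, so deterioration before leaving would be recorded and used by the MAR model. The plan also has contrasts at earlier visits and adjustment for variables such as sessions attended. All of this stands, and it narrows the concern. It does not remove it: the unseen weights stay unseen, and an undefined judgement made after the data are in decides whether a possibly unfavourable analysis exists at all.

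Four stronger readings are tempting, and the documents do not support them.

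- **That the plan has no MNAR method.** It names a suitable one and reviews reasons for dropout by arm.
- **That most trials with hidden informative dropout would get no MNAR analysis.** The figure depends on the reading of the trigger. With four tests at 5%, equal dropout and the same mix of reasons in all arms, simulation flags about 15–16% of trials, which leaves about 84–85% without the analysis. With 23 tests treated as independent, 1 − 0.95^23 = 69% are flagged by chance, which leaves about 31%. The plan fixes neither reading.
- **That the result would be biased by a known amount.** A grid with p from 20% to 40% and D from 0 to 2.92 kg in either arm spans −1.17 to +1.17 kg (0.40 × 2.92 = 1.17). These ends are corners of assumed values, not bounds.
- **That the bias favours naltrexone.** The pilot's only dropout was on placebo, for personal reasons, so the sign cannot be assumed.

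**Conclusion.** The concern holds as a fault in the stated rule. The MNAR analysis depends on a screen that cannot rule MNAR out and has no criterion. If the screen looks clean, neither week-52 contrast is tested against a departure from MAR. If it is flagged, the imputation as written may only repeat MAR.

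The direction and size of any bias cannot be derived from the documents, and the kg and percentage figures above are illustrations only. The point assumes that the intention-to-treat target includes weight after leaving, which the plan leaves undefined. A MAR mixed model is acceptable as the primary analysis, and nothing here invalidates the trial. This should be corrected because it bears on both primary contrasts and the correction is cheap.

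**What to change.** Keep the MAR mixed model as primary. Replace the trigger and the imputation sentence with one pre-specified MNAR sensitivity analysis, always run for both week-52 contrasts, with its assumptions written down. Two suitable forms are:

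- delta-adjusted pattern-mixture imputation, with the shift increased from 0 until the conclusion changes (tipping point) and allowed to differ by arm; or
- imputation of naltrexone leavers from the placebo arm.

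State whether the target includes weight after leaving. Use the by-arm review of patterns, timing and reasons to judge which shifts are plausible, not whether to run the analysis. Keep the completer analysis as a supplement.

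The cost is a few sentences and modest programming, with no new data and no change to the primary model. The range of shifts is a judgement that must be justified, and the sensitivity estimates may be less favourable than the MAR estimate.

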As Chair, do you have any real or apparent protocol-specific conflict of interest between yourself and the sponsor of the research project, or its competitor or any interest in any intervention and/or method tested in the project that might compromise this research project?

Yes (provide a description of that interest in a separate letter addressed to the HIC)
 No

I assure the HIC that the principal investigator and all members of the research team are qualified by education, training, licensure and/or experience to assume participation in the conduct of this research trial. I also assure that the principal investigator has departmental support and sufficient resources to conduct this trial appropriately.

Chair Name (PRINT) and Signature

Date

Department

YNHH Human Subjects Protection Administrator Assurance Statement

Required when the study is conducted solely at YNHH by YNHH health care providers.

As Human Subject Protection Administrator (HSPA) for YNHH, I certify that:

- I have read a copy of the protocol and approve it being conducted at YNHH.
- I agree to notify the IRB if I am aware of any real or apparent institutional conflict of interest.
- The principal investigator of this study is qualified to serve as P.I. and has the support of the hospital for this research project.

YNHH HSPA Name (PRINT) and Signature

Date

SECTION V: RESEARCH PLAN

1. Statement of Purpose: State the scientific aim(s) of the study, or the hypotheses to be tested.

The purpose of this study is to determine the efficacy of two doses of naltrexone (25mg & 50mg) versus placebo for weight and health risk reduction in 200 obese individuals with severe mental illness treated with an antipsychotic medication.

Hypothesis 1: Subjects receiving naltrexone 25mg and 50mg for one year will reduce weight, and improve body mass index (BMI) and waist circumference, at a greater level than the subjects who receive placebo.

Hypothesis 2: Both naltrexone arms will improve health risk markers: serum lipid profile, fasting glucose, and glycosylated hemoglobin (HbA1c) better than placebo.

Exploratory Aim: To determine the optimum effective dose of naltrexone to counteract antipsychotic induced weight gain.

2. Background: Describe the background information that led to the plan for this project. Provide references to support the expectation of obtaining useful scientific data.

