Subjects will be randomized to active Naltrexone 25mg, Naltrexone 50mg, and placebo groups in a 1:1:1 ratio using a computer randomization procedure at the CMHC research pharmacy, blind to both research team and subjects. Separate randomization schedules will be applied based on gender, and antipsychotic agent to yield an equal number of male and female subjects in each arm. This is to control for possible differential gender and racial/ethnicity specific effects of Naltrexone on weight as well as differences brought on by higher and lower weight liability medications.

Subjects will take the study medication daily for 52 weeks. Subjects will be seen weekly for the first 4 weeks of the study, thereafter they will be seen on a bi-weekly (every other week) basis to be assessed (i.e. weight, side effect check, paper questionnaires) throughout the remaining 48 weeks of treatment. Compliance will be monitored by pill counts as well as 25mg riboflavin added to the capsules which provides florescence to urine under Wood's lamp (UV or black light). Subjects will be given a study identification card listing the fact that they may be taking naltrexone and this card will include the study emergency cell phone number which will be available 24 hours a day, 7 days per week in case of an emergency.

The study is planned to be run at the Connecticut Mental Health Center (CMHC) and its affiliated satellite clinics throughout the greater New Haven area.

All participants will be carefully assessed with physical examination and laboratory findings, any medical problems that need immediate attention will be referred to each participant's own primary care physician. All potential subjects will meet with study staff for intake and evaluation sessions to determine eligibility prior to enrollment.

A description of assessments is given below:

1) Intake interview including demographics, clinical history, Structured Clinical Interview for DSM-IV (**SCID**) to ascertain diagnosis. 2) Urine toxicology (**Utox**) screen to rule out substance use. The initial sample will also be sent to the lab to confirm opiate results for safety purposes and a follow-up sample will be taken immediately before randomization to study medication to ensure it is negative for opiates; continued random testing will occur at the discretion of the study physician throughout the trial along

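### The two primary week-52 dose contrasts have no decision rule and no multiplicity adjustment; if either dose alone may support the claim, the overall type 1 error is 9.1% rather than 5%

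*Combined protocol and SAP*

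**What the plan says.** All references are to Section V of the combined protocol and SAP.

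- **Primary tests** (item 12, Hypothesis Testing): "However, the primary contrasts will be each dose compared with control at 52 weeks". With 25 mg and 50 mg arms and one placebo arm, that is two primary tests.
- **Significance level** (item 12, opening paragraph): "For all analyses, an alpha threshold of 5% (two-sided) will be used to test for statistical significance".
- **Multiplicity** (item 12, end of the Hypothesis Testing paragraph): "Type 1 error for secondary outcomes will be adjusted using the Bonferroni correction". The primary contrasts are not mentioned.
- **Role of the interaction** (item 12, Hypothesis Testing): "The interaction between treatment and time will be modeled and interpreted using graphical displays and post-hoc contrasts on least square means". Nothing makes the week-52 contrasts conditional on a significant interaction.
- **Hypotheses** (item 1, Statement of Purpose): Hypothesis 1, which covers weight, begins "Subjects receiving naltrexone 25mg and 50mg for one year will reduce weight". Hypothesis 2, on lipids, glucose and HbA1c, begins "Both naltrexone arms will improve health risk markers". Both are written as expectations, not as rules for declaring success.
- **Allocation** (item 3, Research Plan): three arms, "and placebo groups in a 1:1:1 ratio".

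**The concern.** Two doses of one drug are compared with a shared placebo group, and both comparisons are called primary. A reader needs to know what follows when one is significant and the other is not. The text does not settle this. Referring to each dose separately fits a rule under which one dose is enough; naming both doses in Hypothesis 1 fits a rule under which both must succeed.

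The two rules have different error rates. Under the either-dose rule, two unadjusted 5% tests give two chances of a false claim for naltrexone. Under the both-doses rule there is no inflation, but less chance of success. The authors did consider multiplicity, since they prescribe Bonferroni for secondary outcomes, yet the tests that carry the main conclusion have no such protection. If the rule is left open, it may be chosen once the results are known.

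**Working it through.** **Inputs from the protocol**

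- Two-sided 5% per test (item 12): critical value 1.96, so 2.5% in the direction of benefit. The 2.5% is not printed; it is half of the stated 5%.
- Two primary contrasts against one placebo arm (item 12).
- 1:1:1 allocation (item 3). With equal arms of size n and common variance σ², each contrast has variance 2σ²/n and their covariance is σ²/n, so the correlation is ρ = 1/2.

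No effect size, standard deviation, power or dropout figure is given, and none is needed for the error rates.

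**Check of the stated level.** For one contrast, 2 × P(Z > 1.96) = 0.050, with 0.025 in favor. This reproduces the plan's 5%.

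**Neither dose effective** (Z₁, Z₂ standard bivariate normal, ρ = 0.5)

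| Rule | Formula | Result |
|---|---|---|
| Either dose, in favor | 1 − P(Z₁ < 1.96, Z₂ < 1.96) | 0.0454 |
| Either dose, both directions | 1 − P(\|Z₁\| < 1.96, \|Z₂\| < 1.96) | 0.0907 |
| Both doses, in favor | P(Z₁ > 1.96, Z₂ > 1.96) | 0.0046 |

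The first and third rows agree with each other: 0.025 + 0.025 − 0.0046 = 0.0454. A simulation of 2 million trials with 67/67/66 subjects and t tests gave 0.0450 in favor and 0.0902 in both directions.

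**Sensitivity to ρ.** If unequal numbers at week 52 moved ρ to between 0.4 and 0.6 (an assumed range), the either-dose error would be 0.0466 to 0.0438 in favor and 0.0932 to 0.0875 in both directions.

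**Only one dose ineffective.** A false finding for that dose has probability 0.025 in favor under the either-dose rule. Under the both-doses rule, a false joint claim has at most that probability. Neither case is inflated.

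**If an overall test were a gate.** A two-degree-of-freedom test of the three arms at 5%, followed by 5% contrasts, was simulated as a stand-in. It gave 0.021 in favor and 0.041 in both directions. The protocol writes no such gate.

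**Adjusted tests.** Dunnett for two contrasts with ρ = 0.5 has critical value 2.212, or two-sided 0.027 per contrast; the overall error is 0.050 in both directions and 0.025 in favor. Holm tests the smaller p-value at 0.025 (critical value 2.241) and, if that is significant, the other at 0.05.

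**Power, illustration only.** Start from an assumed unadjusted power per contrast, so that the mean of Z is m = 1.96 + z(power): 2.80 for 80%, 3.24 for 90%. Dunnett power is Φ(m − 2.212). Holm power for dose 1 is P(Z₁ > 2.241, or Z₁ > 1.96 and Z₂ > 2.241).

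| | 80% unadjusted | 90% unadjusted |
|---|---|---|
| Dunnett, per dose | 72% | 85% |
| Holm, per dose, other dose has same effect | 76% | 88% |
| Holm, per dose, other dose has no effect | 71% | 84% |
| At least one dose, Holm, same effect | 85% | 94% |
| Both doses at 5% each, same effect | 69% | 83% |

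**The case against.** The strongest reply is that no inflation has been shown. The 5% in item 12 is a per-test level; the protocol nowhere promises a 5% error rate across the two doses. If the doses are separate questions, each keeps its own 5%, and the exploratory aim of finding the optimum dose is compatible with that view. The nearest wording to a rule, Hypothesis 1, names both doses; read as a joint claim, it gives 0.46%. If the contrasts were meant to follow a significant interaction, the stand-in calculation also shows no inflation.

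Much of this stands. A reader might infer that the plan runs at a 9.1% error rate. The documents do not support that, because the figure needs a rule that they do not state. A reader might equally infer that Hypothesis 1 already requires both doses, or that the interaction is a gate. Neither is written as a rule. The explicit word for both arms is in Hypothesis 2, which concerns secondary markers, and the sentence on the interaction sets no condition.

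What does not stand is that the omission is harmless. The two arms are doses of one drug against one placebo group, and the stated purpose is that drug's efficacy. As written, the plan runs two unadjusted primary tests and would let a single significant dose be reported as success.

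It would also go too far to say that the gap cannot be repaired after unblinding. The contrasts, time point and model family are specified, so anyone with both p-values can apply Holm. Only the pre-declared rule is lost.

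**Conclusion.** The concern holds in conditional form. The plan has two primary contrasts at two-sided 5% each, with no decision rule, order, gate or adjustment. If either dose alone may support a claim and neither works, the chance of a false primary finding is 9.1% in both directions, or 4.5% in favor of naltrexone. If both must be significant, it is 0.46% in favor when neither works and at most 2.5% when one does. The figures rest on equal arms, common variance and the normal approximation; plausible departures in the correlation move the 9.1% only to between 8.8% and 9.3%.

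This is a gap worth closing before unblinding, but not one that by itself invalidates the trial: the inflation depends on the reading, each dose's own error is as stated, and a later adjustment is possible, though it would not be pre-specified.

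**What to change.** Add to the Hypothesis Testing paragraph, before unblinding, that the two primary week-52 contrasts are tested with Holm at an overall two-sided 5%, so that a claim on either dose is valid. Dunnett is an acceptable alternative. If the sponsor intends the joint claim of Hypothesis 1, state instead that both contrasts must be significant at two-sided 5%, with no adjustment. In either case, say that the week-52 contrasts do not depend on the interaction test, unless a gate is intended, in which case write it down.

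The text change is one or two sentences and an option in the analysis code; no new data are needed. The price is power. From an assumed 80% per dose, Holm leaves 71% to 76% and Dunnett 72%; requiring both doses gives 69% if they have the same effect. Restoring 80% per dose under Dunnett would take about 19% more subjects: (2.212 + 0.842)² / (1.960 + 0.842)² = 1.19. Because the protocol gives no power calculation, whether 200 subjects can absorb this loss cannot be judged from the documents.
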